3.2.7. Concomitant Medications and Non-Drug Therapy/Procedures

3.2.7.1. Concomitant Medications

Concomitant medications are those medications taken on or after the initiation of IMP. These medications include those medications started before the initiation of IMP and continuing post Day 1 through the last dose of IMP. Medications that start after the last dose of IMP will be classified as taken post last dose and will not be considered as concomitant and will be noted as ‘Post’ in the data listing. All medications will be recorded in the CONCOMITANT MEDICATIONS CRF.

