## 2 INTRODUCTION

### 2.1 Trial Rationale

CVL-865 (formerly known as PF-06372865) is a potent ligand of the allosteric benzodiazepine (BZD) site of the  $\gamma$ -aminobutyric acid type A (GABAA) receptor, which is being developed for the treatment of epilepsy. The aim of this trial is to evaluate the long-term safety and tolerability of CVL-865 as adjunctive treatment of adult patients with drug-resistant focal onset seizures who completed the Maintenance Phase of Trial CVL-865-SZ-001.

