**Table 4 Dosing Schedule**

	Double-blind Titration Phase a		Maintenance Phase a	Taper Phase a		
	Day 1	Day 8		Day 15	Day 380	Day 387
Duration	2 weeks		52 weeks	3 weeks		
Dose in Trial CVL-865-SZ-001						
Placebo	5 mg BID	12.5 mg BID	25 mg BID	17.5 mg BID	10 mg BID	5 mg BID
CVL-865 7.5 mg BID	12.5 mg BID	17.5 mg BID	25 mg BID	17.5 mg BID	10 mg BID	5 mg BID
CVL-865 25 mg BID	25 mg BID	25 mg BID	25 mg BID	17.5 mg BID	10 mg BID	5 mg BID
Not applicable b			17.5 mg BID b	10 mg BID	5 mg BID	2.5 mg BID

Abbreviations: BID = twice daily; IMP = investigational medicinal product.

a Quantity of IMP dispensed at each visit will accommodate  $\pm 3$ -day visit windows so subjects can remain on existing dose until next in-clinic visit.

b Subjects who had their dose reduced to 17.5 mg BID due to tolerability reasons during the Maintenance Phase.

Subjects are to continue treatment with at least 1 and up to a maximum of 3 concurrent AEDs (as permitted; see [Table 6](#) for prohibited medications). The type and dosage of the concurrent AEDs may be adjusted per investigator discretion to optimize seizure control and/or tolerability during the Treatment Period and/or Follow-up Period.

Subjects will continue to record all seizures and the presence or absence of all seizure types experienced, in addition to recording the dosing with CVL-865 and AEDs and the use of seizure rescue medication in the electronic diary (eDiary) each day during the trial.

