## 6.5 Prior and Concomitant Therapy

### 6.5.1 *Prior and Concomitant Medications*

The investigator will record all medications and therapies (including vaccines, over-the-counter or prescription medicines, vitamins, and/or herbal supplements) taken by the subject from the time of signing the informed consent through the end of the evaluation period (defined as the time period during which subjects are evaluated for primary and/or secondary objectives) on the eCRF. The investigator will also record all medications and therapies taken by the subject for treatment of an AE or which caused an AE until the end of the trial (defined as the last date of contact or date of final contact attempt) on the eCRF.

For concomitant medications, the following will be recorded in the eCRF: medication, indication, dose, frequency, route, start date and end date. For concomitant therapy, the following will be recorded in the eCRF: therapy, indication, start date, and end date.

All subjects should be counselled on the importance of taking background medications as prescribed.

The medical monitor should be contacted if there are any questions regarding concomitant or prior therapy.

[Table 6](#) lists all medications prohibited during the trial, including exceptions where appropriate.

Use of BZDs during trial is permitted except in cases specifically defined below.

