## 9.2 Sample Size Determination

The sample size is not based on statistical power considerations. The trial population will be derived from eligible subjects from the double-blind, proof-of-concept

Trial CVL-865-SZ001. Approximately 120 subjects are expected to complete Trial CVL-865-SZ-001 and be eligible for enrollment in Trial CVL-865-SZ-002.

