5.12.2. Non-AED Concomitant Medications and Non-Drug Therapy/Procedures

Prior and concomitant medications taken during the study will be coded using the World Health Organization (WHO) dictionary (Version: Global B3, March 2024 or higher). Each concomitant medication will be classified as either an anti-epileptic (AED) or a non-AED medication. Non-AED prior and concomitant medications will be summarized by frequency of drug classification and generic drug name. Prior and concomitant medications will be presented in a data listing. The drug classification will be the anatomic therapeutic chemical (ATC) classification 4. If this classification is not present, the next available classification will be utilized.

Prior and concomitant non-drug therapy/procedures will be coded using MedDRA Version 27.1 or higher. Concomitant non-drug therapy/procedures will be summarized by frequency of SOC and PT. Prior and concomitant non-drug therapy/procedures will be presented in a data listing.

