5.12.8. Modified Clinical Institute Withdrawal Assessment – Benzodiazepines (mCIWA-B)

The clinician-observed assessment section has been removed for the modified version of CIWA-B, and the total scores of mCIWA-B ranges from 1 to 68. The total score will be summarized descriptively at the scheduled visits. Change from on-treatment Day 379 assessment will be included.

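### Benzodiazepines and AEDs started after the last dose are listed but not tabulated, and mCIWA-B is summarized without regard to benzodiazepine use, so withdrawal may be understated

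*SAP*

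**What the plan says.** **Classification.** SAP 3.2.7.1: "Medications that start after the last dose of IMP will be classified as taken post last dose and will not be considered as concomitant". These drugs are marked Post "in the data listing. All medications will be recorded in the CONCOMITANT MEDICATIONS CRF".

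**Medication tables.** There are two. SAP 5.12.2: "Non-AED prior and concomitant medications will be summarized by frequency of drug classification and generic drug name". SAP 5.12.3 does the same for concomitant AEDs. SAP 3.2.8 describes the carried-over Rescue Protocol but plans no summary of rescue use, and the SAP plans no table of eDiary benzodiazepine use.

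**Withdrawal endpoint.** mCIWA-B is listed under the primary objective (Protocol Section 3, SAP Table 2). SAP 5.12.8: "The total score will be summarized descriptively at the scheduled visits", with change from the on-treatment Day 379 assessment. Nothing there refers to benzodiazepines or AEDs.

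**What the protocol allows.** Section 6.5.1: "Use of BZDs during trial is permitted except in cases specifically defined below". Section 4.1 lets investigators adjust concurrent AEDs "to optimize seizure control and/or tolerability during the Treatment Period and/or Follow-up Period". Section 2.1 describes CVL-865 as a "potent ligand of the allosteric benzodiazepine (BZD) site".

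**The concern.** A scale of benzodiazepine-withdrawal symptoms is being used to judge what happens when a benzodiazepine-site drug is stopped. If a subject starts a benzodiazepine while coming off CVL-865, the symptoms that the scale counts may be relieved and later scores lowered. Subjects with more symptoms are plausibly the likelier ones to be given one, so the loss would fall where the rise was largest.

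Under the plan, a reader of the tables sees a mean mCIWA-B change at each visit but cannot see how many subjects had started or increased a benzodiazepine by then. For drugs first taken after the last dose, no table shows that they were taken at all. A low mean at Days 407 and 428 could reflect little withdrawal or relieved withdrawal, and the planned summaries would not separate the two.

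**Working it through.** **1. Is there a stated figure to reproduce?** No. The trial is descriptive, and Protocol 9.2 says "The sample size is not based on statistical power considerations". The check is a reading of the rules, a count of visits and an illustration.

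**2. Where each kind of use ends up** (SAP 3.2.7.1, 5.12.2, 5.12.3, 5.12.8)

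| Use of a benzodiazepine or AED | SAP class | In a medication table? | Considered in the mCIWA-B summary? |
|---|---|---|---|
| In use earlier, or started during taper | Concomitant | Yes, but not by phase | No |
| In use earlier, increased after the last dose | Concomitant | The drug, but not the increase | No |
| Newly started after the last dose | Post | No, listing only | No |

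The last dose is the last date on which any IMP was received (SAP 4.1.12), so taper days come before it. The tabulation gap is confined to the third row, plus the unseen increase in the second. The mCIWA-B gap covers all three rows.

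**3. Which mCIWA-B assessments are off drug.** The scheduled days are 379, 386, 393, 400, 407 and 428 (Protocol Table 3). The taper days differ between the documents: Protocol Table 4 shows steps at Days 380 and 387, while SAP Table 1 shows Days 386, 393 and 400. Both readings were tried, with 7-day steps assumed.

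- Protocol Table 4: third step 387 + 7 = Day 394, last dose 394 + 6 = Day 400.
- SAP Table 1, with its days read as step starts: last dose 400 + 6 = Day 406.

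Either way, Days 386, 393 and 400 fall on or before the last dose, and Days 407 and 428 fall after it. That is 2 of the 5 assessments after the Day 379 reference. The nominal window for Post drugs is 428 − 400 = 28 days or 428 − 406 = 22 days.

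Subjects who do not taper have their Visit 17 assessments about 30 days after the last dose (Protocol 7.3). For them, every drug newly started after stopping is Post. SAP Table 6 also assigns off-treatment early-termination and unscheduled assessments up to Day 389 to the Day 386 row, so that row can hold off-drug scores too.

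**4. How far a mean could move (all inputs assumed).** Let D be the rise in a withdrawing subject, w the share who withdraw with symptoms, t the share of those treated, and r the part of the rise that treatment removes.

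Observed mean rise = D × w × (1 − t × r), so the proportion lost is t × r.

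| D (points) | w | Untreated, D × w | t = 50%, r = 50% | t = 50%, r = 100% |
|---|---|---|---|---|
| 5 | 10% | 0.5 | 0.375 | 0.25 |
| 5 | 30% | 1.5 | 1.125 | 0.75 |
| 10 | 10% | 1.0 | 0.75 | 0.50 |
| 10 | 30% | 3.0 | 2.25 | 1.50 |

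At t = 50% the loss is 25% to 50%. At t = 25% and r = 50% it is 12.5%. The mean rise reaches zero only at t = r = 100%. The formula gives every withdrawing subject the same D; if treated subjects had the larger rises, the loss would be greater.

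**The case against.** A reader might infer that treated withdrawal will be reported as no withdrawal. The documents do not support that. It would take treatment of every withdrawing subject with complete effect, and scores taken before treatment starts are untouched. Withdrawal symptoms reported as adverse events are also tabulated: TEAEs run through the last follow-up contact (SAP 3.2.1.3 and 5.12.1).

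A reader might also infer that no table covers treatment begun in the taper or follow-up weeks. That is wrong for the taper, where a new drug is concomitant and enters the tables, although not by phase. Drugs started later are flagged subject by subject in the listing.

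Three further objections have weight:

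- **Direction.** A new AED after an anti-seizure drug is stopped may simply serve seizure control, which Protocol 4.1 expressly allows. The scale includes fatigue, and Protocol 2.2 notes that benzodiazepines sedate, so some items could rise.
- **Legitimacy of pooling.** Protocol 9.4.1 promised descriptive total scores at scheduled visits, and the SAP delivers them. Summarizing scores whatever drugs were taken is a valid description.
- **The split.** It conditions on an event that withdrawal itself may cause, so neither group estimates untreated withdrawal.

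These limit the wording and shape the remedy, but the gap remains. An adverse-event table does not show who took a benzodiazepine before a given score, and a listing gives no count. Adverse events are tabulated to the last contact, while drugs newly begun after the last dose are not.

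**Conclusion.** The gap is real but moderate. Benzodiazepines and AEDs newly started after the last dose are in no planned medication table, and mCIWA-B at Days 386 to 428 is summarized without regard to benzodiazepine use. Withdrawal may be understated, most clearly at Days 407 and 428 and in subjects who stop without tapering. The size is unknown because the documents give no usage rate; the 25% to 50% loss rests wholly on the assumed t and r. That the bias is downward assumes that benzodiazepines relieve the symptoms scored and that subjects with more symptoms are likelier to receive them. The documents make this plausible but do not establish it. For AEDs the case is weaker, so they should be reported separately and not counted as treated withdrawal.

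**What to change.** - **SAP 3.2.7.1, 5.12.2 and 5.12.3:** tabulate benzodiazepines started between the last dose and Visit 17, and AEDs started in that window in a separate table. Define benzodiazepines as their own class, because the SAP does not say whether they fall under AED or non-AED.
- **SAP 5.12.8:** keep the pooled summary. Add the number of subjects who started or increased a benzodiazepine since Visit 15/ET, by Taper and Follow-up, from the eDiary and the concomitant-medication CRF. Add a supportive mCIWA-B summary by that status, labelled descriptive, with a note that neither group estimates untreated withdrawal.
- **Dates:** reconcile the taper days in Protocol Table 4 and SAP Table 1, since the last dose decides what is classed as Post.

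The cost is SAP wording and a few descriptive tables. The data are already collected: concomitant medications are recorded through the last visit, and the eDiary runs to Visit 17. Planned diary compliance stops at the last dose (SAP 5.10), so the follow-up counts should state how many subjects had diary data. The main drawback is small subgroups. If all of the approximately 120 expected subjects were assessed and 10% started a benzodiazepine (assumed), that group would be 120 × 0.10 = 12.

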3.2.7.2. Concomitant Non-Drug Therapy/Procedures

Concomitant non-drug therapy/procedures are defined similarly to concomitant medications and will be recorded in the NON-DRUG THERAPY/PROCEDURES eCRF.

3.2.7.3. Prior Medications

Prior medications are those medications taken prior and ended prior to the initiation of IMP. These medications will be recorded in the CONCOMITANT MEDICATION eCRF.

3.2.7.4. Prior Non-Drug Therapy/Procedures

Prior non-drug therapy/procedures are defined similarly to prior medications and will be recorded in the NON-DRUG THERAPY/PROCEDURES eCRF.

3.2.8. Rescue Medicine

All subjects who normally take BZDs for seizure rescue had an individualized Rescue Protocol approved by the Epilepsy Study Consortium (TESC) in use during Trial CVL-865-SZ-001. This Rescue Protocol describes what rescue treatment can be administered in the event the subject requires a BZD. It also includes different scenarios that would prompt immediate medical attention. The rescue protocol will remain in place for this extension protocol.

3.3. Pharmacokinetics

To evaluate the plasma exposure of CVL-865 (and anti-epileptic drug, if appropriate), a single daytime blood sample will be collected at Visits 1, 5, 8, and 11. The date and time of the pharmacokinetic (PK) sample, as well as the time of ingestion of the morning dose of IMP (on the same day), will be recorded in the source documentation.

4. DATA CONVENTIONS AND VISIT WINDOWS

4.1. Data Conventions

4.1.1. Age

Age is the age at the time of informed consent and is as captured on the DEMOGRAPHY eCRF.

4.1.2. Screen Failures

Screen failures are defined as subjects who consent to participate in this clinical trial but are deemed not eligible or withdraw consent prior to receiving IMP in Trial CVL-865-SZ-002. Receiving IMP defined as any IMP taken after the ICF has been signed by the subject.

4.1.3. Study Day 1 (Extension)

Day 1 is the day IMP is first initiated in CVL-865-SZ-002. The extension Day 1 will be referred to as 'Day 1' throughout the document.

4.1.4. Study Day 1 (Double-Blind)

Day 1 is the day IMP is first initiated in CVL-865-SZ-001.

4.1.5. Study Day of an Event (Extension)

Study day of an event is defined relative to Day 1 as:

Study Day = event date – date of Extension Day 1 (+ 1, if event date \geq date of Day 1).

This calculation will result in negative study days for an event occurring prior to the start of IMP and positive study days for an event on or after the start of IMP. There will be no Day 0 value to match the schedule of events.

4.1.6. Days on Study (Extension)

Days on Study is the number of days from Day 1 to the date of completion/discontinuation as recorded on the END OF STUDY CRF.

4.1.7. Days on Study (Double-Blind + Extension)

Days on Study is the number of days from Double-Blind Day 1 to the date of completion/discontinuation as recorded on the END OF STUDY CRF.

4.1.8. Days on IMP (Extension)

Days on IMP is the number of days from Day 1 to the date of last dose of IMP as recorded on the EXPOSURE CRF.

4.1.9. Days on IMP (Double-Blind + Extension)

Days on IMP is the number of days from Double-Blind Day 1 to the date of last dose of IMP as recorded on the EXPOSURE CRF.

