Currently, approximately 290 subjects have been administered CVL-865 in single doses ranging from 0.04 to 100 mg, and in multiple doses ranging from 2.5 mg to 42.5 mg twice daily (BID) administered for a total duration of up to 4 weeks. CVL-865 has been safe and well tolerated.

CVL-865-SZ-001 is a 13-week, placebo-controlled, double-blind trial designed to assess the efficacy, safety, and tolerability profile of CVL-865 as adjunctive treatment in subjects with drug-resistant focal onset seizures. This 57-week, active-treatment, open-label extension trial is designed to assess the safety and tolerability of CVL-865 as adjunctive treatment in subjects with drug-resistant focal onset seizures. This trial is open to subjects who completed the Maintenance Phase in the double-blind Trial CVL-865-SZ-001 and who, in the opinion of the investigator, could potentially benefit from treatment with CVL-865.

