### 3 OBJECTIVES AND ENDPOINTS

Objectives	Endpoints
Primary: To assess the long-term safety and tolerability of CVL-865 as adjunctive therapy in subjects with focal onset seizures	
 
• Nature, frequency, and temporality of treatment-emergent AEs (nonserious and serious), including abuse-related AEs and AEs related to medication handling irregularities
 
• Clinically significant changes in ECGs, vital sign measurements, clinical laboratory assessments, and physical and neurological examination results
 
• Suicidality assessed using the C-SSRS
 
• Withdrawal symptoms assessed using the mCIWA-B
 

Exploratory: To assess the long-term efficacy of CVL-865 as adjunctive therapy in subjects with focal onset seizures	
 
• Focal onset seizure frequency per week over the Maintenance Phase
 
• Seizure freedom
 
• Seizure rate over time
 
• PGI-C score at each trial visit
 
• Change from Baseline in CGI-S score at each trial visit
 

Exploratory: To evaluate the plasma exposure of CVL-865	
 
• Summary listing of CVL-865 concentrations by dose and visit
 

Abbreviations: AE = adverse event; CGI-S = Clinical Global Impression – Severity; C-SSRS = Columbia-Suicide Severity Rating Scale; ECG = electrocardiogram; mCIWA-B = Modified Clinical Institute Withdrawal Assessment – Benzodiazepines; PGI-C = Patient Global Impression of Change.

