## **6 TRIAL TREATMENTS**

Trial treatment is defined as any investigational treatment(s), marketed product(s), placebo, or medical device(s) intended to be administered to a trial subject according to the trial protocol. Investigational medicinal product refers to a pharmaceutical form of any active substance or placebo being tested in this clinical trial and will be used to refer to the trial treatment in this protocol.

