5. STATISTICAL ANALYSIS METHODS

5.1. General Considerations

Descriptive statistical methods will be used to summarize the data from this trial. Unless stated otherwise, the term “descriptive statistics” refers to number of subjects (N), number of observations (n), arithmetic mean, median, standard deviation (SD), first quartile (Q1), third quartile (Q3), minimum, and maximum for continuous data, and frequencies and percentages for categorical data. Certain figure presentations will include the standard error of the mean (SE). The term “treatment group” refers to treatment assignment in Trial CVL-865-SZ-001: Placebo, 7.5 mg BID CVL-865, 25 mg BID CVL-865 and assignment in Trial CVL-865-SZ-002: 25 mg BID CVL-865. All data collected from subjects who sign the informed consent form, including screen failures, will be included in data listings. Unless otherwise noted, the data listings will be sorted first by treatment, subject number and then by date within each subject number.

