5.8. Exposure to Treatment

The number of subjects who received IMP, treatment compliance, cumulative exposure to IMP (Double-Blind + Extension), days on IMP (Double-Blind and Extension), prematurely discontinued, and reason for IMP discontinuation will be summarized.

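### Combined Days on IMP counts SZ-001 placebo days as exposure, and no aggregate TEAE table by onset time is planned although temporality is in the primary endpoint

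*SAP*

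**What the plan says.** **Exposure.** SAP 4.1.9 defines the combined duration as "Days on IMP is the number of days from Double-Blind Day 1 to the date of last dose of IMP". SAP 4.1.4 fixes the starting point for all arms alike: "Day 1 is the day IMP is first initiated in CVL-865-SZ-001". The protocol background describes the parent study: "CVL-865-SZ-001 is a 13-week, placebo-controlled, double-blind trial designed to assess the efficacy". SAP 5.1 lists placebo among the arms that subjects come from: "treatment assignment in Trial CVL-865-SZ-001: Placebo, 7.5 mg BID CVL-865, 25 mg BID CVL-865". Protocol section 6 gives the term a wide meaning: "Investigational medicinal product refers to a pharmaceutical form of any active substance or placebo being tested in this clinical trial". An extension-only duration is defined separately in SAP 4.1.8: "Days on IMP is the number of days from Day 1 to the date of last dose of IMP". SAP 5.8, headed as exposure to treatment, lists among its outputs "cumulative exposure to IMP (Double-Blind + Extension), days on IMP (Double-Blind and Extension". It does not exclude placebo days or state a split by SZ-001 arm.

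**Timing of adverse events.** The first primary endpoint in protocol section 3 reads "Nature, frequency, and temporality of treatment-emergent AEs (nonserious and serious", and SAP section 2 repeats it. SAP 5.12.1 tabulates TEAEs by preferred term, system organ class and intensity, with subsets for serious, related, fatal, special-interest and discontinuation events. All use one window from Day 1 to the last follow-up contact. It adds a presentation by dose at onset, and listings. Protocol 9.4.1 adds no summary by onset time. The phase boundaries in SAP 4.2 are set for efficacy data and have no Follow-up row.

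**The concern.** Protocol 2.2 says that earlier multiple dosing lasted at most 4 weeks, so time on CVL-865 is one of the main things this trial adds. A reader of an exposure table will take combined days as time on drug. For subjects from the placebo arm, and in any pooled column, that reading is too high.

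On adverse events, nature and frequency each have an aggregate analysis and temporality has none. One incidence over the whole window cannot show whether events cluster at the start, accrue late in a 52-week Maintenance Phase, or begin after the last dose. Those patterns mean different things for the matters the protocol itself raises: haematologic decreases, sedation-type events and withdrawal.

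**Working it through.** The plan gives no figure for either point. The one stated quantity to reproduce is the Treatment Period: 2 + 52 + 3 = 57 weeks, 57 × 7 = 399 days, consistent with Visit 16 on Day 400.

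**1. Exposure**

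Inputs:
- E, extension days on IMP: 399 for a completer, from the schedule. For an early leaver I take a last dose on Day 183 (the Visit 8 day) as an example.
- D, SZ-001 dosing days before rollover: not given. The protocol says only that SZ-001 is a 13-week trial. I assume 8 to 13 weeks, with 13 as a ceiling, so D = 8 × 7 = 56 to 13 × 7 = 91 days.
- There is no gap between the trials: extension Visit 1 is the same day as SZ-001 Visit 4 (protocol Table 2, footnote b).

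Formulas for a subject from the placebo arm: count under 4.1.9 = D + E; days on CVL-865 = E; excess = D; relative excess = D / E.

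| Subject | E | D + E | D / E |
|---|---|---|---|
| Completer | 399 | 455 to 490 | 56/399 = 14.0% to 91/399 = 22.8% |
| Last dose Day 183 | 183 | 239 to 274 | 56/183 = 30.6% to 91/183 = 49.7% |

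In a pooled column the mean excess is the placebo share × D. The documents do not give the share. At one-third it is 18.7 to 30.3 days. For shares from one-quarter to one-half it runs from 0.25 × 56 = 14.0 to 0.5 × 91 = 45.5 days.

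**2. What dose at onset reveals about timing**

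From protocol Table 4, the phases in which each BID dose is scheduled:

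| Dose | From placebo | From 7.5 mg | From 25 mg | Reduced to 17.5 mg |
|---|---|---|---|---|
| 2.5 mg | – | – | – | Taper |
| 5 mg | Titration, Taper | Taper | Taper | Taper |
| 10 mg | Taper | Taper | Taper | Taper |
| 12.5 mg | Titration | Titration | – | – |
| 17.5 mg | Taper | Titration, Taper | Taper | Maintenance |
| 25 mg | Maintenance | Maintenance | Titration, Maintenance | – |

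The last column shows maintenance and taper after a dose reduction. For full-dose subjects from placebo or 7.5 mg, 25 mg BID is a single block of 52/57 = 91.2% of planned dosing weeks. For those from 25 mg it is 54/57 = 94.7%. An event in the first maintenance month and one in the last fall in the same cell.

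After the last dose there is no current dose. Planned follow-up is 428 − 400 = 28 days, or 28/428 = 6.5% of the planned TEAE window. SAP 3.2.1.3 counts these events as treatment-emergent.

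**The case against.** **On exposure.** The label is days on IMP, and the protocol's IMP includes placebo, so the derivation does what its name says. That stands: a reader might infer that 4.1.9 contradicts the protocol's definition, and it does not. The difficulty is the use of the figure as exposure.

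A reader might also infer that true time on CVL-865 will go unreported. The documents do not support that. The wording in 5.8 changes within one sentence from a plus sign to the word and, so it can be read as promising both the combined and the extension-only counts. For subjects from placebo, the extension-only count is their time on CVL-865. Columns by SZ-001 arm are also plausible given 5.1, and would confine placebo days to one arm's column plus any total. But 5.8 says neither, whereas 5.9 does specify treatment group for medical history.

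Nor do the documents support an inference that adverse event rates are biased. TEAEs are counted from extension Day 1 and no exposure-adjusted rate is planned. Combined cumulative dose in mg is also not inflated if placebo counts as 0 mg, which SAP 4.1.17 leaves unstated.

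**On timing.** Protocol 9.4.1 calls frequency and severity the primary safety analysis, and the endpoint does not prescribe a table by onset interval. Timing is also not ignored. Study Day is derived, all events are listed, and protocol 8.4.6.1 requires narratives with time to onset and offset for listed abuse-related terms. Laboratory, vital-sign, ECG and mCIWA-B results are summarised by visit. This stands, but the first three are subject-level and the by-visit summaries cover measurements and scores, not TEAEs.

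A reader might infer that dose at onset says almost nothing about phase. That goes too far. Even for the former 25 mg arm, 52 of the 54 weeks at 25 mg BID (96.3%) are maintenance, and that arm has no dose change at Day 15. What the display cannot do is divide maintenance. Nor is it certain to lose follow-up events: its categories are not specified, and an off-IMP row would capture them, mixed with any dose interruptions.

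**Conclusion.** Both parts hold within limits, and both should be corrected before database lock.

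1. Applied as written, 4.1.9 overstates time on CVL-865 for every subject from the placebo arm by the length of that subject's SZ-001 dosing. The size rests on the assumed 8 to 13 weeks; the direction does not. The effect reaches the combined exposure summary and nothing else.
2. Temporality is a named component of the primary endpoint without an aggregate TEAE analysis. This rests on the text of 5.12.1 and the dosing table and needs no outside assumption. The firm gap is early against late onset within maintenance. Identification of follow-up events depends on whether an off-IMP category is added.

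No hypothesis is tested, so no inferential result is affected. The patient-level data are adequate; what needs changing is one derivation and one output.

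**What to change.** 1. In SAP 4.1.9, define combined days on CVL-865 from the first active dose: Double-Blind Day 1 for the 7.5 mg and 25 mg arms, extension Day 1 for the placebo arm. In 5.8, state that this is tabulated by SZ-001 arm and overall, beside the extension-only count of 4.1.8. If the sponsor keeps the present derivation as well, label it as including placebo.
2. In SAP 5.12.1, add one TEAE table by onset interval: Titration, maintenance blocks of the sponsor's choice, Taper and Follow-up, with the number at risk in each. Extend the SAP 4.2 boundaries to adverse events and add a Follow-up row. Those boundaries already start Taper at early termination, so subjects who leave early would be placed by actual phase and not by calendar day.

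Cost: one changed derivation and one added table, from data already collected. Exposure figures for the former placebo arm and for all subjects pooled become lower.
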